3.3.2. Microbiological Outcome Status

- 1 Microbiological outcome status for the primary analysis is evaluated at Visit 2 and is defined as follows:
 - Microbiological Cure: *N. gonorrhoeae* not detectable by culture from all anatomical sites that had detectable *N. gonorrhoeae* at Visit 1.
 - Microbiological Failure: *N. gonorrhoeae* detectable by culture from at least one anatomical site that had detectable *N. gonorrhoeae* at Visit 1.
 - Non-evaluable: At least one of the following:
 - Subject did not return for Visit 2, or
 - Culture results at Visit 2 were not available for any reason, or
 - Subject could not be evaluated for microbiological outcome status for any other reason.
- 2 For the analysis of secondary objective 1, microbiological outcome status at each anatomical site is evaluated at Visit 2 and is defined for a particular anatomical site as follows:
 - Microbiological Cure: *N. gonorrhoeae* not detectable by culture at the particular anatomical site that had detectable *N. gonorrhoeae* at Visit 1.
 - Microbiological Failure: *N. gonorrhoeae* detectable by culture at the particular anatomical site that had detectable *N. gonorrhoeae* at Visit 1.
 - Non-evaluable: At least one of the following:
 - Subject did not return for Visit 2, or
 - Culture results at Visit 2 were not available for any reason, or
 - Subject could not be evaluated for microbiological outcome status for any other reason.

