6.3.2. Efficacy Analyses

All efficacy analyses will be performed in the Per Protocol (PP), microbiological Intent-to Treat (micro-ITT) and Intent-to-Treat (ITT) analyses populations.

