6.3.2.1. Intent-to-Treat Analysis (ITT) Population

The ITT analysis population includes all enrolled subjects, regardless of whether they received study treatment or were compliant with the administration procedures or schedule.

Subjects with non-evaluable outcome status will be included in the ITT analysis population and classified as microbiological failures. Subjects who receive any treatment other than the study medication for their *N. gonorrhoeae* infection will be included in all efficacy analyses as treatment failures. Subjects who discontinued early from the study with lack of treatment effect being the documented reason for discontinuation will be included as microbiological failures. Subjects who vomited within 1 hour of administration will be included as microbiological failures.

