6.3.2.2. Microbiological Intent-to-Treat (micro-ITT) Population

For the primary analysis, the micro-ITT population includes all enrolled subjects who have wild type *gyrA* serine 91 *N. gonorrhoeae* isolated from the rectum or urogenital site on Day 1 culture. Subjects with infections at multiple anatomic sites are included as long as one of the infected sites is the rectum or urogenital site. Subjects with infections at multiple anatomic sites must be wild-type at each culture-positive site to be included in the primary analysis.

Subjects with non-evaluable outcome status will be included in the micro-ITT population and classified as microbiological failures. Subjects who discontinued early from the study with lack of treatment effect being the documented reason for discontinuation will be included as microbiological failures. Subjects who vomited within 1 hour of administration will be included as microbiological failures.

For the analysis of secondary objective 1, subjects need to have wild type *gyrA* serine 91 *N. gonorrhoeae* isolated on Day 1 culture at the particular anatomical site being assessed. The results at the other anatomical sites will not be considered when determining a subject's eligibility into each of the site-specific populations.

There will be four micro-ITT populations identified:

- Primary micro-ITT population
- Rectal micro-ITT population
- Urogenital micro-ITT population
- Pharyngeal micro-ITT population

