6.5. Missing Data

For the primary analysis, subjects with non-evaluable outcome status will be included in the micro-ITT analysis population and classified as microbiological failures. Subjects who discontinued early from the study with lack of treatment effect being the documented reason for discontinuation will be included as microbiological failures.

For the PP analyses of the primary outcome measure, subjects who have a non-evaluable outcome status, including subjects who did not return for Visit 2, whose culture results at Visit 2 were not available for any reason, or could not be evaluated for microbiological outcome status for any other reason are excluded.

For the secondary analysis of microbiological cure at each anatomic site using site-specific micro-ITT analysis populations, subjects with non-evaluable outcome status at the particular anatomic site will be included in analyses and classified as microbiological failures.

Subjects who discontinued early from the study due to a lack of treatment effect are counted in all analysis populations as microbiological failures.

For secondary outcome of the sensitivity of the *gyrA* assay for detection of ciprofloxacin-susceptible *N. gonorrhoeae* infections, only specimens with determinate results for both the *gyrA* assay and the culture-based antimicrobial susceptibility test will be included. If either the *gyrA* assay or the culture-based antimicrobial susceptibility test results are indeterminate or missing, the specimen will be excluded from the analysis.

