8.3. Exploratory Efficacy Analyses

The proportion of subjects infected with *gyrA* serine 91 genotype *N. gonorrhoeae* with microbiological cure at Visit 2 will be summarized by demographic (sex, age, race, ethnicity) and clinical characteristics (symptomatic status and re-exposure status at follow up by anatomic sites). Age will be broken into two categories based on the median age: Age < median and Age ≥ median for each analysis population. The microbiological cure rate will be calculated separately for each category. See [Table 21](#) and [Table 26](#). The analyses by demographics will be repeated on the infection level, as well (see [Table 22](#), [Table 23](#), [Table 24](#), and [Table 25](#)).

The genomic analyses of identification and characterization of non-*gyrA* gene-dependent mechanisms of ciprofloxacin resistance by genotyping and whole genome sequencing of nucleic acid isolated from uncured subjects at Visit 2 will be described in a separate statistical analysis plan.

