The denominator for rate estimates is based on the number of subjects enrolled and eligible for the micro-ITT population for the particular anatomical site and microbiological outcome.

Implementation Notes: The Micro-ITT Population will be based on the anatomical site.

Tables with similar format:

Table 20: Antimicrobial Susceptibility of *N. Gonorrhoeae* Isolates by Specimen Type and Microbiological Outcome at Visit 2—PP population

Implementation Notes: The Micro-ITT Population will be based on the anatomical site.

Table 21: Microbiological Cure Rate by Demographic Characteristics and Analysis Population

Characteristic	Analysis Population											
	ITT Population				micro-ITT Population				PP Population			
	Number of Subjects with Microbiological Cure, n	Number of subjects, N	Cure Rate, %	Cure Rate 95% CI, %	Number of Subjects with Microbiological Cure. n	Number of subjects, N	Cure Rate, %	Cure Rate 95% CI, %	Number of Subjects with Microbiological Cure, n	Number of subjects, N	Cure Rate, %	Cure Rate 95% CI, %
Male	x	x	xx.x	xx.x, 100	x	x	xx.x	xx.x, 100	x	x	xx.x	xx.x, 100
Female	x	x	xx.x	xx.x, 100	x	x	xx.x	xx.x, 100	x	x	xx.x	xx.x, 100
Age < Median	x	x	xx.x	xx.x, 100	x	x	xx.x	xx.x, 100	x	x	xx.x	xx.x, 100
Age >= median	x	x	xx.x	xx.x, 100	x	x	xx.x	xx.x, 100	x	x	xx.x	xx.x, 100
American Indian/ Alaskan Native	x	x	xx.x	xx.x, 100	x	x	xx.	xx.x, 100	x	x	xx.x	xx.x, 100
Asian	x	x	xx.x	xx.x, 100	x	x	xx.x	xx.x, 100	x	x	xx.x	xx.x, 100
Hawaiian/ Pacific Islander	x	x	xx.x	xx.x, 100	x	x	xx.x	xx.x, 100	x	x	xx.x	xx.x, 100
White	x	x	xx.x	xx.x, 100	x	x	xx.x	xx.x, 100	x	x	xx.x	xx.x, 100
Multi-Racial	x	x	xx.x	xx.x, 100	x	x	xx.x	xx.x, 100	x	x	xx.x	xx.x, 100
Other/Unknown	x	x	xx.x	xx.x, 100	x	x	xx.x	xx.x, 100	x	x	xx.x	xx.x, 100
Non-Hispanic	x	x	xx.x	xx.x, 100	x	x	xx.x	xx.x, 100	x	x	xx.x	xx.x, 100
Hispanic	x	x	xx.x	xx.x, 100	x	x	xx.x	xx.x, 100	x	x	xx.x	xx.x, 100
Not Reported/ Unknown	x	x	xx.x	xx.x, 100	x	x	xx.x	xx.x, 100	x	x	xx.x	xx.x, 100

Tables with similar format:

Table 22: Microbiological Cure Rate by Demographic Characteristics and Analysis Population — All Infections

Table 23: Microbiological Cure Rate by Demographic Characteristics and Analysis Population — Urethral Infections

Table 24: Microbiological Cure Rate by Demographic Characteristics and Analysis Population — Rectal Infections

Table 25: Microbiological Cure Rate by Demographic Characteristics and Analysis Population — Pharyngeal Infections

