Implementation Notes: The analysis populations will be based on the anatomical site.

Table 26: Microbiological Cure Rate by Clinical Characteristics—Micro-ITT Population

Statistics	Cervical		Urethral		Rectal		Pharyngeal		All Anatomical Sites	
	Symptomatic Status		Symptomatic Status		Symptomatic Status		Symptomatic Status		Symptomatic Status	
	Symptomatic	Asymptomatic	Symptomatic	Asymptomatic	Symptomatic	Asymptomatic	Symptomatic	Asymptomatic	Symptomatic	Asymptomatic
Number of Infections with Microbiological Cure, n	x	x	x	x	x	x	x	x	x	x
Number of Infections, N	x	x	x	x	x	x	x	x	x	x
Microbiological Cure Rate	xx.x	xx.x	xx.x	xx.x	xx.x	xx.x	xx.x	xx.x	xx.x	xx.x
Microbiological Cure Rate 95% CI, %	xx.x, 100	xx.x, 100	xx.x, 100	xx.x, 100	xx.x, 100	xx.x, 100	xx.x, 100	xx.x, 100	xx.x, 100	xx.x, 100
	Re-exposure at Follow up		Re-exposure at Follow up		Re-exposure at Follow up		Re-exposure at Follow up		Re-exposure at Follow up	
	Sex with Protection	Sex without Protection	Sex without Protection	Sex without Protection	Sex without Protection	Sex without Protection	Sex without Protection	Sex without Protection	Sex without Protection	Sex without Protection
Number of Infections with Microbiological Cure, n	x	x	x	x	x	x	x	x	x	x
Number of Infections, N	x	x	x	x	x	x	x	x	x	x
Microbiological Cure Rate, %	xx.x	xx.x	xx.x	xx.x	xx.x	xx.x	xx.x	xx.x	xx.x	xx.x
Microbiological Cure Rate 95% CI, %	xx.x, 100	xx.x, 100	xx.x, 100	xx.x, 100	xx.x, 100	xx.x, 100	xx.x, 100	xx.x, 100	xx.x, 100	xx.x, 100

Implementation Notes: The Micro-ITT Population will be based on the anatomical site.

Table 27: Summary of Categorical Demographic and Baseline Characteristics by Site—All Enrolled Subjects

Variable	Characteristic	AIDS Healthcare Foundation (N=X)		Los Angeles LGBT Center (N=X)		San Francisco Department of Public Health (N=X)		Philadelphia Department of Public Health (N=X)		University of Mississippi Medical Center (N=X)		Louisiana State University (N=X)		University of California, San Diego Antiviral Research Center (N=X)		Whitman-Walker Health (N=X)		All Subjects (N=X)	
		n	%	n	%	n	%	n	%	n	%	n	%	n	%	n	%	n	%
Sex	Male	x	xx	x	xx	x	xx	x	xx	x	xx	x	xx	x	xx	x	xx	x	xx
Ethnicity	Female	x	xx	x	xx	x	xx	x	xx	x	xx	x	xx	x	xx	x	xx	x	xx
	Not Hispanic or Latino	x	xx	x	xx	x	xx	x	xx	x	xx	x	xx	x	xx	x	xx	x	xx
	Hispanic or Latino	x	xx	x	xx	x	xx	x	xx	x	xx	x	xx	x	xx	x	xx	x	xx
	Not Reported	x	xx	x	xx	x	xx	x	xx	x	xx	x	xx	x	xx	x	xx	x	xx
Race	Unknown	x	xx	x	xx	x	xx	x	xx	x	xx	x	xx	x	xx	x	xx	x	xx

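### SAP Table 26 plans cure by symptomatic status in micro-ITT only, although SAP 6.3.2 promises three populations; if missing Visit 2 cultures differ by symptoms, the table would show a cure difference that is not one of efficacy

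*SAP*

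**What the plan says.** SAP 6.3.2 sets a general rule: "All efficacy analyses will be performed in the Per Protocol (PP), microbiological Intent-to Treat (micro-ITT) and Intent-to-Treat (ITT) analyses populations". SAP 8.3, under exploratory efficacy analyses, plans cure at Visit 2 by demographics and by "clinical characteristics (symptomatic status and re-exposure status at follow up by anatomic sites". It names no narrower population for the clinical characteristics.

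The shells treat the two halves differently. The demographic one, "Table 21: Microbiological Cure Rate by Demographic Characteristics and Analysis Population", has ITT, micro-ITT and PP columns. The clinical one is "Table 26: Microbiological Cure Rate by Clinical Characteristics—Micro-ITT Population", with the same title in the list of tables and in the mock-up, and it has no companion for another population. Its implementation note makes the micro-ITT population site-specific. Its rows are infections cured, infections in total, cure rate and confidence interval.

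SAP 3.3.2 makes an outcome non-evaluable if, among other reasons, "Subject did not return for Visit 2, or" if the Visit 2 culture result is unavailable. For the micro-ITT population, SAP 6.3.2.2 says: "Subjects with non-evaluable outcome status will be included in the micro-ITT population and classified as microbiological failures". For the site-specific micro-ITT analyses, SAP 6.5 says that "subjects with non-evaluable outcome status at the particular anatomic site will be included in analyses and classified as microbiological failures". SAP 6.3.2.3 leaves such subjects out of PP.

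**The concern.** There are two parts. The first is consistency. SAP 6.3.2 allows no exceptions and SAP 8.3 states none, so a programmer working from the text would produce three populations and one working from the shell would produce one. The population left out includes PP, in which the primary test is done.

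The second is interpretation. A micro-ITT cure rate with non-evaluable counted as failure combines two things: how often the infection was cleared, and how often a Visit 2 culture was obtained. That is a defensible conservative summary for one group. When two groups stand side by side, a difference in the second component looks the same as a difference in the first. Return for Visit 2 could plausibly depend on symptoms. Protocol 5.3.2 says that subjects who tolerated the drug and never came back are not contacted for repeat testing, so those outcomes are not recovered later. A reader of Table 26 alone could take a difference in attendance for a difference in how well ciprofloxacin works in asymptomatic infection.

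**Working it through.** **Inputs from the plan** (SAP section 5, matching Protocol 11.2): assumed cure rate 98%; 25% culture negative at baseline; 10% excluded from PP; PP target 257; enrolment 381.

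**The plan's own figures reproduce.**
- Enrolment: 257 / (0.75 × 0.90) = 380.7, rounded up to 381.
- Power at 257: the smallest number of cures whose modified Jeffreys lower bound reaches 0.95 is 250. The exact binomial probability of at least 250 cures at a true rate of 98% is 85.4%, against a stated value of about 85%.

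None of these figures is in dispute. They supply the 98% used below and the size of the group.

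**Size of micro-ITT.** 381 × 0.75 = 285.75, about 286 subjects. Of these, 10%, about 29, are planned PP exclusions for all reasons together.

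**Formula.** Let p be the true cure rate and m the non-evaluable share, with missingness unrelated to outcome within the group.
- Micro-ITT rate shown = p × (1 − m)
- Rate among evaluable infections = p
- With the same p in both groups, the gap shown in micro-ITT = p × (difference in m)

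At p = 0.98, each 1-point difference in m gives 0.98 points of apparent cure difference.

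**Range.** The documents give no non-evaluable share by symptomatic status, so every pair below is assumed.

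| Non-evaluable, group A / B | Micro-ITT rate shown, A / B | Gap (points) |
|---|---|---|
| 10% / 10% | 88.2% / 88.2% | 0 |
| 8% / 12% | 0.98 × 0.92 = 90.2% / 0.98 × 0.88 = 86.2% | 3.9 |
| 5% / 10% | 0.98 × 0.95 = 93.1% / 0.98 × 0.90 = 88.2% | 4.9 |
| 5% / 15% (extreme) | 0.98 × 0.95 = 93.1% / 0.98 × 0.85 = 83.3% | 9.8 |

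Under the same assumption, a version restricted to evaluable infections would show 98% in both groups in every row.

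**The reverse case.** A real difference can also be hidden. True 94% with 4% missing gives 0.94 × 0.96 = 90.2%. True 98% with 8% missing gives 0.98 × 0.92 = 90.2%.

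**Scope.** The arithmetic concerns the symptomatic-status half of Table 26. Re-exposure is asked at follow-up, so a subject who never returns has no re-exposure status, and the shell has no column for such subjects.

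**The case against.** The strongest reply is that little depends on this table. It serves an exploratory objective, and SAP 6.4 already says that the study lacks the power for subgroup analyses. No difference, test or p-value between symptom groups is planned; each column has its own one-sided interval. Precision is also low. If the 286 subjects split evenly, 143 and 143, the standard error of a 90.2% against 86.2% difference is √[(0.902 × 0.098 + 0.862 × 0.138) / 143], about 3.8 points. The milder gap is therefore about one standard error, before any split by anatomical site. All of this stands and limits the weight of the point.

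It can also be said that SAP 6.3.2 is a general sentence from which the SAP departs elsewhere. SAP 8.2 puts the assay's sensitivity and predictive value in ITT, and SAP 8.2.1 puts the MIC summaries in micro-ITT and PP. Those departures, however, are stated in the body text. For Table 26 the restriction appears only in a shell title.

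Four stronger readings are tempting, and the documents do not support them.

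- A reader might infer that attendance does differ by symptoms, so that Table 26 will mislead. No attendance figures by symptom status are given, and equal shares give no gap.
- A reader might treat the planned 10% as the non-evaluable rate. It covers every PP exclusion. SAP Table 4 also lists eligibility failures, non-compliance, contraindicated or other antibiotic use and out-of-window visits. Pairs that average 10% in equal groups are therefore at the ceiling of the planning assumption.
- A reader might infer that nothing in the plan separates attendance from failure. Listing 7 shows non-evaluable as its own outcome by subject and anatomical site, and Listing 12 gives symptoms by subject and visit. The two can be matched by hand; what is missing is a summary.
- A reader might take PP as the clean measure of drug effect. PP conditions on returning in window with an evaluable culture, so it is biased too if return depends on whether the infection cleared.

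**Conclusion.** The inconsistency is in the text and does not depend on any assumption: SAP 6.3.2 and 8.3 imply three populations for cure by clinical characteristics, and the only shell delivers one.

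The effect on interpretation is conditional. It arises only if non-evaluable shares differ by symptomatic status, and then amounts to 0.98 points per point of difference at a 98% true cure rate. That is 3.9 points for 8% against 12%. The 9.8 points for 5% against 15% is an extreme assumed case, not an expectation. The statement that an evaluable-only version would show no gap rests on missingness being unrelated to outcome within each group. PP therefore complements micro-ITT and does not replace it.

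Severity is minor. The table is exploratory and descriptive, and the primary PP conclusion does not depend on it.

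**What to change.** - Produce Table 26 in the site-specific PP populations as well.
- In the micro-ITT version, add a row to each column that counts non-evaluable infections separately from culture-positive failures. This row shows directly whether the shares differ, and it does not need the PP assumption about missingness.
- For ITT, either add that version too, as SAP 6.3.2 requires, or state the exception in SAP 6.3.2 and 8.3. ITT alone would not answer the interpretive question, because there too "Subjects with non-evaluable outcome status will be included in the ITT analysis population and classified as microbiological failures".

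No new data are needed. The cost is one repeated table (two if ITT is added), one row and possibly one sentence. The downside is one more exploratory table with small cells.

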7.1 Visit 1, Day 1 (Screening/Enrollment)

Screening and enrollment will occur at the same clinic visit. Potential subjects will be informed about the study and invited to participate. Subjects who are interested in the study will be asked to sign a consent form that will describe the purpose of the study, the procedures to be followed, the risks and benefits of participating, and will include a separate section for consent to store samples for future use. A copy of the consent form will be given to the subject and this fact will be documented in the CRF.

The following will be performed for subjects who give informed consent:

1. Demographic information including age, sex, and gender will be collected from the subject
2. Eligibility criteria will be reviewed with the subject
3. Discuss pertinent medical history for assessment of specific symptoms that are potentially related to fluoroquinolone use as described in section 9, Assessment of Safety, and sexual history will be obtained by interview of subjects to assure eligibility. Concomitant infections will be reviewed.
4. Review of signs and symptoms within the past 7 days
5. All new antibiotics or concomitant medications contraindicated with ciprofloxacin taken in the 30 days prior to signing the informed consent will be recorded on the appropriate data collection form
6. Targeted physical exam
7. Speculum exam for females
Note: Women diagnosed with BV by local standard test at Visit 1 will receive treatment for BV at Visit 2 according to local standard of care.
8. Urine pregnancy test for females of childbearing potential
9. One swab for *N. gonorrhoeae* culture and one swab for NAAT and *gyrA* serine 91 genotype from the throat*
10. One swab for *N. gonorrhoeae* culture and one swab for NAAT and *gyrA* serine 91 genotype from the rectum*
11. One swab for *N. gonorrhoeae* culture from the urethra (males)*
12. Urine specimen for NAAT and *gyrA* serine 91 genotype (males)*
13. Cervical swab for *N. gonorrhoeae* culture (females)*
14. Cervical or vaginal swab for NAAT and *gyrA* serine 91 genotype (females)*
*Note 1: Only at the suspected infected anatomical site based on prior test results or other sites as clinically indicated
*Note 2: *GyrA* assay is required only if NAAT is positive

-

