7.2 Visit 2, Day 5-10 (Test of Cure Visit)

Subjects will have the following:

1. Interim medical history for assessment of specific symptoms that are potentially related to fluoroquinolone use as described in section 9, Assessment of Safety, and interim sexual history
2. Review of signs and symptoms at site of infection since the previous visit
3. Review of new antibiotics or concomitant medications contraindicated with ciprofloxacin
4. Targeted physical exam
5. One swab for *N. gonorrhoeae* culture and one swab for NAAT and *gyrA* serine 91 genotype from the throat*
6. One swab for *N. gonorrhoeae* culture and one swab for NAAT and *gyrA* serine 91 genotype from the rectum*
7. One swab for *N. gonorrhoeae* culture from the urethra (males)*
8. Urine specimen for NAAT and *gyrA* serine 91 genotype (males)*
9. Cervical swab for *N. gonorrhoeae* culture (females)*
10. Cervical or vaginal swab for NAAT and *gyrA* serine 91 genotype (females)*
 - ***Note 1:** Repeat samples to be collected only from those anatomical sites swabbed for *N. gonorrhoeae* culture or NAAT at Visit 1
 - ***Note 2:** *GyrA* assay is required only if NAAT is positive
11. Reminder to bring sex partners in for testing and treatment, if needed
12. Reminder that test results will be provided to subjects by phone call (Visit 3, Day 11-14)

Women diagnosed with bacterial vaginosis (BV) will receive treatment according to local standard of care.

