7.3 Visit 3, Day 11 to 14 (Test of Cure Results)

1. Test results will be provided to subjects by phone call.
2. Subjects whose Visit 2 (Day 5-10) *N. gonorrhoeae* culture and NAAT results are negative will have completed participation in the study; no further follow-up is required.
3. Subjects who are *N. gonorrhoeae* culture positive or NAAT positive will be referred for standard of care treatment for *N. gonorrhoeae*.
4. Reminder to bring sex partners in for testing and treatment, if needed

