9. SAFETY EVALUATION

9.1. Demographic and Other Baseline Characteristics

Summaries of age, sex, ethnicity, and race will be presented by site for all enrolled subjects (ITT population) and PP population ([Table 27](#), [Table 28](#)). Ethnicity is categorized as Hispanic or Latino, or not Hispanic and not Latino. Race is categorized as American Indian or Alaska Native, Asian, Native Hawaiian or Other Pacific Islander, Black or African American, White, Multi-Racial, or Unknown. In accordance with NIH reporting policy, subjects may self-designate as belonging to more than one race (Multi-Racial) or may refuse to identify a race (Unknown), the latter reflected in the electronic Case Report Form (eCRF) as “No” to each racial option. Age will be summarized by site for all enrolled subjects and PP population ([Table 29](#), [Table 30](#)). A summary of signs and symptoms of *N. gonorrhoeae* will be presented by visit ([Table 31](#)).

Baseline and follow-up sexual history will be summarized for all enrolled subjects (ITT population) ([Table 32](#), [Table 33](#)).

Individual subject listings (Appendix 3) will be presented for all demographics and baseline characteristics ([Listing 8](#)), sexual history ([Listing 9](#), [Listing 10](#), [Listing 11](#)), and *N. gonorrhoeae* symptomatology ([Listing 12](#)).

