N is the number of subjects assessed for signs/symptoms at the particular visit.

'n' represents the number of subjects who reported each sign or symptom at the Visit(s) indicated.

The same subject may be counted at all visits;

*Only some subjects have data at Visit 3 due to the protocol amendment.

1 The denominator of the percentage is the number of subjects for each visit.

2 The denominator of the percentage is the number of males for each visit.

3 The denominator of the percentage is the number of females for each visit.

Table 32: Summary of Baseline Categorical Sexual History—ITT population

Sexual History Interview Question	Value	All Subjects (N=X)	
		n	%
1. What is your gender identity?	Man	x	xx
	Woman	x	xx
	Trans male/Trans man	x	xx
	Trans female/Trans woman	x	xx
	Genderqueer/Gender non-conforming	x	xx
	Multiple	x	xx
	Other	x	xx
	Refused to Answer	x	xx
2. What is your sexual orientation?	Heterosexual/Straight	x	xx
	Homosexual/gay/lesbian	x	xx
	Bisexual	x	xx
	Other	x	xx
	Refused to Answer	x	xx
3. Do you have sex with men, women, transgender men, transgender women, or multiple genders?	Men	x	xx
	Women	x	xx
	Trans male/Trans man	x	xx
	Trans female/Trans woman	x	xx
	Multiple	x	xx
	Refused to Answer	x	xx
4. Have you had sex (vaginal, anal, or oral) in the past 30 days?	Yes	x	xx
	No	x	xx
	Refuse to answer	x	xx

N=Number of all enrolled subjects

Table 33: Summary of Follow-up Categorical Sexual History—All Enrolled Subjects

Sexual History Interview Question	Value	Visit 2 (N=X)		Unscheduled Visit (N=X)		All Subjects (N=X)	
		n	%	n	%	n	%
1. Have you had sex (vaginal, anal, or oral) since the last visit?	Yes	x	xx	x	xx	x	xx
	No	x	xx	x	xx	x	xx
	Refuse to answer	x	xx	x	xx	x	xx
2. Have you had vaginal intercourse since the last visit?	Yes	x	xx	x	xx	x	xx
	No	x	xx	x	xx	x	xx
	Refuse to answer	x	xx	x	xx	x	xx
If Yes for question 2, did you use a condom with vaginal intercourse ¹	No	x	xx	x	xx	x	xx
	Always	x	xx	x	xx	x	xx
	Sometimes	x	xx	x	xx	x	xx
	Unknown	x	xx	x	xx	x	xx
	Refuse to answer	x	xx	x	xx	x	xx
3. Have you given oral intercourse since the last visit?	Yes	x	xx	x	xx	x	xx
	No	x	xx	x	xx	x	xx
	Refuse to answer	x	xx	x	xx	x	xx
If Yes for question 3, did you use a condom or barrier with oral intercourse? ²	No	x	xx	x	xx	x	xx
	Always	x	xx	x	xx	x	xx
	Sometimes	x	xx	x	xx	x	xx
	Unknown	x	xx	x	xx	x	xx
	Refuse to answer	x	xx	x	xx	x	xx
4. Have you received oral intercourse since the last visit?	Yes	x	xx	x	xx	x	xx
	No	x	xx	x	xx	x	xx
	Refuse to answer	x	xx	x	xx	x	xx

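### If Visit 2 follows Protocol 7.2, symptom percentages in SAP Table 31 can fall from Visit 1 to Visit 2 without any treatment effect, because subjects not asked about a site stay in its denominator

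*SAP*

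**What the plan says.** Protocol 7.1 (Visit 1) lists: "Review of signs and symptoms within the past 7 days". It names no anatomical site. Protocol 7.2 (Visit 2) lists: "Review of signs and symptoms at site of infection since the previous visit".

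SAP 9.1 plans the table in one line: "A summary of signs and symptoms of *N. gonorrhoeae* will be presented by visit". The shell is Table 31 in SAP Appendix 1, with columns for Visits 1, 2 and 3. Its footnotes set the denominators:

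- Column N: "N is the number of subjects assessed for signs/symptoms at the particular visit".
- Footnote 1, on the six throat and anorectal rows: "The denominator of the percentage is the number of subjects for each visit".
- Footnote 2, on the three male urogenital rows: "The denominator of the percentage is the number of males for each visit". Footnote 3 does the same with females for the four female rows.
- The row for any symptom has no denominator footnote.

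On the Visit 3 column a footnote says: "Only some subjects have data at Visit 3 due to the protocol amendment". In the current Protocol 7.3, Visit 3 is a results call: "Test results will be provided to subjects by phone call".

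**The concern.** Anatomical scope and recall period both change between two columns that share one set of row labels. The denominators do not follow the change in scope. Under Protocol 7.2 as worded, a subject with urogenital infection only is not asked at Visit 2 about the throat or rectum, yet counts in the denominator for sore throat and anorectal pain, and so appears symptom-free there. The throat rows are the most exposed: inclusion criterion 3 requires infection at a non-pharyngeal site, so throat infection is only ever additional. The sex-specific rows share the problem. Rectal-only infection is eligible, so a man with rectal infection alone sits in the denominator for urethral discharge.

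No other planned table reports gonorrhea symptoms after treatment. In a single-arm trial a reader is likely to take a fall from Visit 1 to Visit 2 as symptom response, when part of it may come from the question asked.

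**Working it through.** The plan states no figure for Table 31, so there is nothing to reproduce. The check is algebraic, and every rate below is an assumption.

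**Scope.** For one site, let f be the share of the denominator infected there, si the symptom rate in those infected there, and su the rate in those not infected there. Suppose treatment changes nothing.

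- Visit 1, all sites asked: f × si + (1 − f) × su
- Visit 2, infected site only, same denominator: f × si
- Difference: (1 − f) × su

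| f | si | su | Visit 1 | Visit 2 | Fall (points) |
|---|---|---|---|---|---|
| 0.30 | 0.20 | 0 | 6.0% | 6.0% | 0 |
| 0.30 | 0.20 | 0.05 | 9.5% | 6.0% | 3.5 |
| 0.30 | 0.20 | 0.10 | 13.0% | 6.0% | 7.0 |
| 0.30 | 0.20 | 0.20 | 20.0% | 6.0% | 14.0 |
| 0.90 | 0.60 | 0.10 | 55.0% | 54.0% | 1.0 |

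Over f from 0.1 to 0.9 and su from 0 to 0.20, the largest fall is (1 − 0.1) × 0.20 = 0.18, or 18 points, and the smallest is 0. This scope effect can lower Visit 2 but cannot raise it.

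**Recall.** Visit 1 covers 7 days. Visit 2 falls on Day 5 to 10 and dosing is on Day 1, so it covers 5 − 1 = 4 to 10 − 1 = 9 days. At an assumed constant daily onset of 1%, the share with any onset is 1 − 0.99^7 = 6.8% over 7 days, 1 − 0.99^4 = 3.9% over 4 and 1 − 0.99^9 = 8.6% over 9. The recall change can therefore move Visit 2 down or up. Symptoms that lasted briefly after dosing and then cleared also count at Visit 2, which pushes it up.

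**With site-specific denominators.** If both columns are limited to subjects infected at the site, both equal si when treatment changes nothing, and the scope effect is 0. The recall difference remains.

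**The case against.** The strongest objection is that the documents do not settle what the form recorded at Visit 2. The signs and symptoms row in Protocol Appendix A and SAP Table 2 is marked at Visits 1 and 2 without the site footnote that the swab rows carry. Listing 12 shows the same throat, anorectal and genital fields for both visits. If every field was asked at Visit 2, the scope effect disappears. That all sites are asked at Visit 1 is likewise inferred from the absence of a limit. This objection stands, and it is why the point is conditional on Protocol 7.2 being followed as written.

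The second objection concerns weight. Table 31 comes under baseline characteristics in SAP 9.1. No test, interval or change from baseline is attached to it, and symptom response is not among the outcome measures. SAP 3.3.7 and Table 26 already handle symptomatic status by infected site, and Listing 12 gives the subject-level data. This also stands: the consequence is one of interpretation only. It does not remove the mismatch, because Table 26 reports cure by baseline symptoms rather than symptoms after treatment.

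A reader might also fault the Visit 3 columns of Tables 31 and 34 as a different set of subjects. They are a subset, but both tables say so and give a visit-specific N. They are correct as labelled, and moving them would be a matter of preference.

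**Conclusion.** The Visit 1 and Visit 2 percentages in Table 31 are not like for like, and a fall between them cannot be read as a treatment effect. If Visit 2 is done as Protocol 7.2 says, the scope change alone can lower a row by (1 − f) × su: 0 to 18 percentage points over the assumed ranges. The true size is unknown, because the documents give neither f nor su.

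A reader might infer that symptoms must fall after treatment by construction. The documents do not support that. The effect is zero if subjects not infected at a site have no symptoms there, it is small where most are infected there, and the recall change can offset it. Very large relative falls, such as 90% at f = 0.10 or 60% at f = 0.40, follow from 1 − f only if su equals si, meaning that symptoms have nothing to do with the infected site.

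Nor is the all-subjects denominator universal: it applies to six of the 13 symptom rows, and the other seven use males or females. The culture-based primary endpoint and all planned tests are untouched.

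**What to change.** In Table 31, report each site's symptoms at Visits 1 and 2 among subjects with infection at that site at Visit 1 who were assessed at both visits, and use that number as the denominator. Take infection as culture-confirmed, following SAP 3.3.7, and add a supplementary row that includes NAAT-positive sites. Label the columns with their recall periods: 'past 7 days' and 'since Visit 1'. State in a footnote what was asked at Visit 2. All-subject counts can stay as a secondary panel, so that symptoms at other sites are not hidden. The Visit 3 columns of Tables 31 and 34 can stay where they are.

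This removes the scope effect whatever the form asked, and pairing removes the difference between those seen at Visit 1 and those who returned. It changes only a shell and its footnotes; no new data are needed. The cost is smaller denominators, most of all for the throat and rectum. Protocol 11.2 expects 25% of enrolled subjects to be culture negative at baseline, and the culture-confirmed rows lose them; the supplementary row recovers those with a positive NAAT.
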